4.3 Concomitant Therapies

A concomitant medication is any drug or substance administered between the signing of the informed consent and the EOS/ET Visit. The use of concomitant therapies or procedures must be recorded on the subject's eCRF, according to instructions for eCRF completion. Adverse events related to administration of these therapies or procedures must be documented in the appropriate eCRF.

Other than the medications listed in Section 4.3.1, medications that are used as the standard of care for SCD will be allowed during the study.

Use of HU/HC is allowed during the study. However, subjects receiving should maintain a stable dose throughout the study.

A COVID-19 vaccination is to be recorded as concomitant medication.

4.3.1 Prohibited Medications and Therapies

Treatment with the following is not allowed during the study:

- Non-study rifaximin (e.g., commercial rifaximin, XIFAXAN® 550 mg tablets), rifampin or other rifamycin derivatives are prohibited within 30 days of providing consent, and throughout the study.
- Initiation of treatment with HU/HC, voxelotor, crizanlizumab, or L-glutamine.
- COVID-19 vaccination.
- Gene therapy for SCD.
- Initiation of a chronic transfusion program (pre-planned series of transfusions for prophylactic purposes).
- Enrollment in any other drug, biologic, or device clinical study or treatment with an approved therapy for investigational development or unapproved investigational drug under development is not allowed.
- Chronic antibiotic use throughout the study is prohibited. A short-course of antibiotic therapy (\leq 7 days; non-rifamycin and non-quinolone classes only) to treat infections such as sinusitis, urinary tract infections, etc. or for dental therapy prophylaxis is permitted. Longer courses of therapy will require the permission of the Sponsor.
- Treatment with CYP3A4 inhibitors/inducers, P-glycoprotein (P-gp) inhibitors/inducers, and organic anion transporting polypeptide (OATP1B1/B3) inhibitors shown in [Appendix 3](#).
- Use of proton pump inhibitors (PPIs).

4.3.2 Concomitant Procedures

A concomitant procedure is any therapeutic intervention (eg, surgery/biopsy, physical therapy) or diagnostic assessment (eg, blood gas measurement, bacterial cultures) performed between the time the subject is enrolled in the study and the EOS/ET Visit.

Subjects are not to receive a stem cell transplant during the study.

Subjects are not to undergo elective surgeries during the study.

4.4 Females of Reproductive Potential

There are no adequate and well controlled studies in pregnant women. Rifaximin has been shown to be teratogenic in rats and rabbits at doses that caused maternal toxicity.

Women of childbearing (reproductive) potential must have a negative serum pregnancy test at Visit 1 (Screening) and negative urine pregnancy test at Visit 2 prior to randomization on Day 1. These subjects must agree to use an acceptable method of contraception throughout their participation in the study (see details in [Section 7.12](#)). If a female subject becomes pregnant while on this study, the study drug will be immediately discontinued, and the subject will be followed until the outcome of the pregnancy is known. The pregnancy will be reported to Salix using the guidelines provided in [Section 7.10](#) and [Section 7.11](#).

4.5 Premature Subject Discontinuation

All subjects are free to withdraw from participating in this study at any time for any reason, specified or unspecified, and without prejudice. No constraints will be placed on ordinary subject management, and subjects, when appropriate, will be placed on other conventional therapy upon request or whenever clinically necessary as determined by their physician.

Withdrawal of the subject from treatment with study drug or from the study will be considered, in consultation with the Sponsor, or designee, for any of the following reasons:

- The subject withdraws consent.
- The subject experiences an intolerable AE or SAE.
- The subject experiences CDAD
- The subject enrolls into another interventional clinical study in which an investigational treatment or approved therapy for investigational use is administered.
- The subject becomes pregnant. Study treatment must be discontinued immediately. Report the pregnancy according to the instructions in [Section 7.10](#).
- The subject is unwilling or unable to comply with the protocol.
- At the discretion of the Investigator or Sponsor.

- Investigator decision that it is not in the best medical interest of the subject to continue participation in the investigation.

Prior to discontinuing a subject, every effort should be made to obtain as much follow-up data as possible. Withdrawn or discontinued subjects will undergo early termination procedures per the scheduled assessments for the Early Termination (ET) Visit. AEs will be followed as described in [Section 7.8](#). Subject withdrawals will be documented clearly on the source documents and applicable eCRFs.

Notification of subject withdrawals will be made to the Sponsor, or designee.

4.6 Subject Replacement

Subjects that are withdrawn, terminate the study early (including for an AE), or are lost to follow-up (LTFU) during the study may be replaced to ensure appropriate number of subjects complete the study. The decision to replace a subject will be made in agreement between the Sponsor and Investigator.

5.0 STUDY DRUG FORMULATION AND SUPPLY

Rifaximin ER and DER are supplied as 20 mg capsules. Subjects will be randomized to receive either 40 mg or 80 mg of ER or DER and matching placebo capsules for the duration of the study.

5.1 Packaging and Labeling

Outer packaging and capsules will be packaged and labeled in a manner consistent with the study design and according to applicable national / regional and local regulations for an investigational drug.

Each unit of rifaximin ER and DER capsules and placebo capsules will bear a label that meets applicable laws for an investigational drug, which includes, but is not limited to, the following information:

- Protocol Number
- Kit Number
- A statement reading: “Caution: New Drug Limited by Federal Law to Investigational Use”
- A statement reading, “Manufactured for Salix Pharmaceuticals, Inc., a division of Bausch Health US, LLC”
- Recommended storage conditions.

5.2 Storage and Handling

All study drug will be kept in a locked area with limited access. All units of study drug must be stored at 20°-25° C (68°-77° F) with excursions of 15°-30° C (59°-86° F) permitted. Study drug will be dispensed by qualified study staff only in accordance with the procedures described in this protocol.

5.3 Dosing and Dosing Schedule

Each subject will be dispensed study drug at each visit with enough capsules to dose through their next visit.

During the Treatment Period, eligible subjects will take study drug BID according to their treatment assignment as outlined in [Table 1](#). Dosing will begin on Study Day 1 (Visit 2) and continue through Study Day 29 (Visit 5). Doses will be taken orally with water, and capsule will be swallowed whole. Study participants should be instructed to take the study drug on an empty stomach. The morning (AM) dose should be taken on an empty stomach, and subjects must avoid food for two hours after taking the study drug. The evening (PM) dose should be taken on an empty stomach (at least two hours after the last meal), and subjects must avoid food for two hours after taking the study drug.

On Days 1, 8, 15, and 29, participants will fast for a minimum of 10 hours prior to, and 2 hours after, the morning study drug administration. Water will be restricted from one hour prior to dosing through one hour following dosing, except for the water that will be consumed at dosing. Study drug should be administered with approximately 240 mL of water.

Table 1 Dosing by Treatment Assignment

Dose Group	Formulation	Study Day	Total Number of Capsules	Capsule (mg)	Daily Dose (mg)	No. of Subjects
1	ER	Daily	4 (2 in AM, 2 in PM)	20	80	12
2	DER	Daily	4 (2 in AM, 2 in PM)	20	80	12
3	Placebo	Daily	4 (2 in AM, 2 in PM)	20	-	6
4	ER	Daily	8 (4 in AM, 4 in PM)	20	160	12
5	DER	Daily	8 (4 in AM, 4 in PM)	20	160	12
6	Placebo	Daily	8 (4 in AM, 4 in PM)	20	-	6

Note: AM and PM refer to approximate 12-hour period between doses

Before any study drug is administered, each subject will be instructed by the Investigator or his/her representative on the proper self-administration of study drug. All unused study drug will be returned to the study site at the next clinic visit.

5.4 Rationale for Dose Selection

The dose and formulation of rifaximin ER and DER formulations selected for this study are based on the safety of these formulations observed in the Phase 1 healthy volunteer study, RBPK 1001 and on the safety of rifaximin in clinical studies supporting the approval of XIFAXAN®. For additional details on the safety of the ER and DER formulations and on XIFAXAN refer to the Investigators' Brochure.

5.5 Study Drug Accountability

All study drug will be kept in a secure, temperature-controlled area with limited access. Investigational drug orders, records of study drug receipt, dispensing, re-dispensing, returned study drug, and running inventory will be examined and reconciled throughout the study. Upon the completion of the study, all material will be subjected to final inspection and reconciliation. Instructions will be provided by the Sponsor regarding final disposition of all study medication in compliance with applicable regulations.

Study drug reconciliation will be conducted during monitoring visits to ensure appropriate receipt, storage, dispensing, and documentation of returned study drug.

5.6 Assessment of Compliance

After study drug is dispensed, the Investigator or his/her representative will count and record the unused study drug capsules that are returned by the subject at each visit. If the subject forgets to return unused study drug at a visit, then compliance will be confirmed after direct questioning of the subject.

6.0 STUDY PROCEDURES AND ASSESSMENTS

The schedule of assessments to be performed during the study is provided in [Appendix 1](#), Schedule of Assessments, and [Appendix 2](#), Schedule for Acquisition of PK Samples. For this study, Day 1 (Visit 2), which is the day of randomization, shall be defined as the subject's Baseline.

Note: Prior to screening study subjects, the flow cytometry assessment (including healthy volunteers) will need to be certified at the laboratory where the assessment will be completed.

In case of situations that prevent a participant from attending a post-baseline study visit, a home health visit may be scheduled, where possible. The home health visit may include an assessment of changes in health and medications, measurement of vital signs and body weight, and checking of study medication compliance. The home health visit may also include all sample collections outlined in the study protocol (PK, hematology and urinalysis samples, urine sample for urine 3-inoxyI sulfate, and blood samples for CANs (if applicable), CD62L, iFABP and LPS).

All documented assessments and laboratory results will be reviewed by the investigator and documented in relevant eCRFs as appropriate.

6.1 Study Schedule by Treatment Visit

6.1.1 Visit 1; Screening (Day -21 to Day -1)

The initial Screening Visit (Visit 1) should be conducted between Days -21 and -1, inclusive. The following procedures are to be completed at Visit 1:

- Obtain informed Consent signed by the subject prior to performing any study evaluations or procedures including asking subjects to discontinue any prohibited medications.
- Record demographics and medical history information. Detailed history of VOCs occurring over the past 12 months will be obtained. This will include collection of treatments for VOCs including drug, dose, route of administration, duration of treatment, and inpatient/outpatient setting.
- Record all opioid use within the 30 days prior to Screening.
- Review Inclusion/Exclusion criteria to ensure subject qualifies for the study.
- Obtain height and weight.
- Obtain vital sign measurements. Vital signs to be collected are blood pressure (BP) heart rate (HR), body temperature, and O₂ saturation.
- Conduct full physical examination.
- Obtain electrocardiogram (ECG; 12-lead).

- Collect blood samples for hematology, blood chemistry, coagulation, and viral testing, and urine sample for urinalysis.
- Perform hemoglobin genotyping (for subjects with unknown genotype).
- Conduct serum pregnancy test for women of childbearing potential (WOCBP).
- Record concomitant medications (record all medications within 30 days of Visit 1).
- Have subjects discontinue use of prohibited medications immediately after Visit 1 (Screening).
- Record adverse events.
- Schedule Visit 2 (Day 1).

6.1.2 Visit 2; Randomization (Day 1)

Randomization will be performed on Day 1. Participants will be in a fasted state. There is no Day 0 in this protocol. The following assessments are to be completed prior to randomization:

- Review Inclusion/Exclusion Review to ensure subject continues to qualify for the study.
- Collect any adverse events since the Screening Visit.
- Collect concomitant medication changes since the Screening Visit. Specifically collect opioid use since Screening.
- Obtain vital sign measurements (BP, HR, body temperature, and O₂ saturation.)
- Conduct symptom-directed physical exam, as needed.
- Obtain ECG (12-lead).
- Collect blood samples for hematology and blood chemistry and urine for urinalysis.
- Collect blood samples for CANs, CD62L, iFABP and LPS.
- Collect urine sample for 3-indoxyl sulfate.
- Confirm negative serum pregnancy test from Screening and conduct urine pregnancy test for WOCBP.
- Query subject and record VOCs that have occurred since Screening.
- If subject continues to meet eligibility requirement, randomize subject.

After randomization, conduct the following assessments:

- Collect pre-dose PK sample.

- Dispense study drug and instruct subject in administration (i.e., number of capsules to take [2 or 4] and timing of BID dosing).
- Have subject administer first dose of study drug.
- Collect PK blood samples at 0.5, 1, 1.5, 2, 3, 4, 5, and 8-hours post-dose.
- Record any concomitant medications.
- Record any adverse events.
- Schedule Visit 3

6.1.3 Visit 3, (Day 8 ±1 day) and Visit 4, (Day 15 ±1 day)

Participants will be in a fasted state. The following assessments are to be completed at Visit 3 and Visit 4:

- Collect any adverse events since Visit 2 or Visit 3.
- Collect concomitant medication changes since Visit 2 or Visit 3. Specifically collect opioid use since Visit 2 or Visit 3.
- Obtain vital sign measurements (BP, HR, body temperature, and O₂ saturation.)
- Conduct symptom-directed physical exam, as needed.
- Collect blood samples for hematology and blood chemistry and urine for urinalysis.
- Collect blood samples for CANs, CD62L, iFABP and LPS.
- Collect urine sample for 3-indoxyl sulfate.
- Query subject and record VOCs that have occurred since Visit 2 or Visit 3.
- Collect unused study drug and review compliance and accountability.
- Collect pre-dose PK sample.
- Dispense study drug and confirm subject's compliance with administration (i.e., number of capsules to take [2 or 4] and timing of BID dosing).
- Have subject administer study drug, record AM or PM dose.
- Collect PK blood samples at 0.5, 1, and 2-hours post-dose.
- Record any concomitant medications.
- Record any adverse events.
- Schedule next Visit (Visit 4 or Visit 5).

6.1.4 Visit 5, (Day 29 ±1 day) EOT/ET Visit

Participants will be in a fasted state. The following assessments are to be completed at the EOT/ET Visit:

- Collect any adverse events since Visit 4.
- Collect concomitant medication changes since Visit 4. Specifically collect opioid use since Visit 4.
- Obtain subject's weight.
- Obtain vital sign measurements (BP, HR, body temperature, and O₂ saturation.)
- Conduct symptom-directed physical exam, as needed.
- Obtain ECG (12-lead).
- Conduct urine pregnancy test for WOCBP.
- Collect blood samples for hematology and blood chemistry and urine for urinalysis.
- Collect blood samples for CANs, CD62L, iFABP and LPS.
- Collect urine sample for 3-indoxyl sulfate.
- Query subject and record VOCs that have occurred since Visit 4.
- Collect pre-dose PK sample.
- Collect unused study drug and review compliance and accountability.
- Have subject administer final dose of study drug.
- Collect PK blood samples at 0.5, 1, 1.5, 2, 3, 4, 5, and 8-hours post-dose.
- Record any concomitant medications.
- Schedule Visit 6.

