3.0 INVESTIGATIONAL PLAN

3.1 Overview of Study Design

Study RBSC2161 is a Phase 2a, randomized, double-blind, placebo-controlled, multicenter study to evaluate the pharmacokinetics (PK), pharmacodynamics (PD) safety and tolerability of rifaximin ER and DER in subjects with SCD. Exploratory assessments of the effect of rifaximin ER and DER on the incidence of VOCs will also be explored.

Approximately 60 subjects who successfully complete the Screening Period will enter the Treatment Period and will be randomized to one of six treatment groups. Approximately 20 study centers are expected to participate in the study.

Objectives and endpoints for the study are provided in [Section 2](#). Assessments of PK/PD and safety, and documentation of VOCs ([Appendix 1](#) and [Section 7.3](#)) will be performed during clinic visits at Baseline (Day 1), Day 8, Day 15, and Day 29 (End of Treatment/Early Termination). All subjects will also complete an End of Study (EOS) Visit 2 weeks later (Day 43; End of Study) for final assessments. Assessments will also be conducted when a subject visits a healthcare facility for treatment of a VOC. If a subject prematurely discontinues treatment, every attempt will be made to obtain EOT and EOS assessments and subjects should be followed until the end of the 43-day trial.

Before study subjects can be screened, the laboratory where the CANs assessment will be performed shall undergo a qualification run. This is to ensure that the flow cytometry assessment for CANs can be performed at the local site as outlined in the Laboratory Manual. The qualification run will be performed with blood from healthy, adult, non-pregnant, and capable volunteers of general good health (and non-sickle cell disease subjects). Approximately 25 healthy volunteers (one per site, or per local lab) is expected to participate. Healthy volunteers will visit the study center once for this assessment (single blood draw) and it should take no more than 30 minutes to complete the testing.

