3.3 Procedures for Breaking the Blind

Subjects, study staff, and the Sponsor will be aware of the dose groups (2 x 20 mg capsules BID or 4 x 20 mg capsules BID) but will be blinded to active or placebo. Only in the case of an emergency, when knowledge of the study drug is essential for the clinical management or welfare of the subject, will the Investigator be allowed to unblind a subject's treatment assignment. To discuss breaking of the blind, the Investigator should contact the Medical Monitor. The Investigator will unblind via an Interactive Response Technology system.

If the Investigator breaks the blind for an individual subject, the reason must be in the subject's source documents and the subject will be removed from the study.

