6.1.8 Visit 9 (Day 43 ± 3 days) EOS Visit

The following assessments are to be completed at the EOS Visit:

- Collect any adverse events since Visit 8.
- Collect concomitant medication changes since Visit 8. Specifically collect opioid use since Visit 8.
- Obtain subject's weight.
- Obtain vital sign measurements (BP, HR, body temperature, and O₂ saturation.)
- Conduct symptom-directed physical exam, as needed.
- Obtain ECG (12-lead) if abnormal findings were observed at Visit 5 (Day 29).
- Conduct urine pregnancy test for WOCBP.

- Collect blood samples for hematology and blood chemistry and urine for urinalysis only if needed for follow-up of AEs or SAEs.
- Collect blood samples for CANs, CD62L, iFABP and LPS.
- Collect urine sample for 3-indoxyl sulfate
- Query subject and record VOCs that have occurred since Visit 5.
- Record any concomitant medications.
- Record any adverse events.
- Discharge subject from study. Follow subject for AEs or SAEs as described in Section 7.7.

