6.1.10 Unscheduled Visit

The Investigator may perform an unscheduled visit at any time during the study at his/her discretion. Assessments performed at an unscheduled visit should be symptom directed.

The following procedures must be performed at all unscheduled visits:

- Collect and record hospital admission and death data.
- Safety laboratory testing. Repeat laboratory testing may be needed based on results from the unscheduled laboratory testing.

- Concomitant medications
- Adverse events

If the subject is discontinued from the study at an unscheduled visit, the visit will be considered Visit 9 (EOT) and all of the EOT assessments should be completed.

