7.3 Adverse Events That Are VOC Endpoint Events

VOC events that are listed in [Table 3](#) are being captured as endpoints and **SHOULD NOT** be reported as an AE or SAE for purposes of this study. These events will not be considered as SAEs for reporting requirements.

Table 3: VOC Events Not Requiring AE/SAE Reporting

Uncomplicated pain crisis*
Acute chest syndrome
Hepatic sequestration
Splenic sequestration
Priapism requiring a visit to a medical facility

* Defined as the occurrence of appropriate symptoms, results in a visit to a medical facility and/or healthcare professional and requires either parenteral or oral opioid or NSAID analgesia, but is NOT classified as an acute chest syndrome, hepatic sequestration, splenic sequestration, or priapism.

All VOCs are to be recorded only once on the “Vaso-Occlusive Event” eCRF page. All VOCs are to be recorded throughout the entire treatment period, up to Visit 5 (Day 29), and should continue until the Follow-Up Visit at Day 43. The Investigator will classify and provide all the following information for each VOC as follows:

- Diagnosis, which will be limited to one of the five pre-defined VOC events as:
 - Uncomplicated pain crisis
 - ACS

- Hepatic sequestration
- Splenic sequestration
- Priapism (requiring a visit to a medical facility)
- Onset date,
- Stop date,
- Action taken (None, Required concomitant medication, Temporarily withheld study drug, Permanent discontinuation of study drug, or Other [explain]),
- Treatment setting,
- Concomitant medications given, and
- Outcome (Recovered without sequelae, Resolved with sequelae, Ongoing, Unknown, Death).

If a subject is hospitalized due to a VOC and during hospitalization develops a non-VOC event that meets the criteria for a SAE, then that event should be reported as a SAE. Any prolongation of a hospitalization due to a non-VOC event (even though they may have initially been hospitalized due to a VOC) is reportable as a SAE in the eCRF.

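### Section 6.1.4 gives the end-of-treatment and early-termination visits one list with an unconditional final dose, and 6.1.10 gives that visit the wrong number

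*Combined protocol and SAP*

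**What the plan says.** Section 6.1.4 is headed as both the Day 29 EOT visit and the ET visit, and gives one list for the two. The list includes a urine pregnancy test where applicable and a pre-dose PK sample. It then says "Have subject administer final dose of study drug", asks for PK samples out to 8 hours, and has the site schedule Visit 6. None of the last three steps carries a condition.

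Three sections send subjects there early:
- Section 4.5: "Withdrawn or discontinued subjects will undergo early termination procedures per the scheduled assessments for the Early Termination (ET) Visit".
- Section 3.1, for premature discontinuation of treatment: "every attempt will be made to obtain EOT and EOS assessments and subjects should be followed until the end of the 43-day trial".
- Section 6.1.10, for a subject discontinued from the study at an unscheduled visit: "the visit will be considered Visit 9 (EOT) and all of the EOT assessments should be completed".

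Other sections stop or hold drug. Under 4.4, if a subject becomes pregnant, "the study drug will be immediately discontinued"; 4.5 and 7.10 say the same in substance. Section 7.8 requires drug to be held while *C. difficile*-associated diarrhea (CDAD) is suspected, and stopped once it is confirmed.

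On numbering, 6.1.8 and Appendix 1 make Visit 9 the Day 43 end-of-study (EOS) visit. Sections 6.1.4 and 6.2.3.5 and Appendix 1 make EOT/ET Visit 5.

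**The concern.** Many subjects who come to an ET visit come because their drug has been stopped. The list written for them tells the site to give another dose. A coordinator working down 6.1.4 meets one instruction, and an investigator applying 4.4 or 7.8 meets the opposite one. At stake are an unneeded dose in someone taken off drug for cause and a day of sampling after it.

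The label in 6.1.10 adds a second ambiguity. A site that goes by the number opens the Day 43 list; a site that goes by the name opens the Day 29 list. Sections 4.3 and 4.3.2 do not help, since they pair ET with EOS.

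**Working it through.** The plan states no figure to reproduce here, and no error rate, power or sample size is involved. The check sets the sections side by side, with a short count of the burden.

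1. **Is there an ET exception anywhere?** Section 6.1.4 has none. Section 6.2.1 and Appendix 2 describe the samples without one. Appendix 1 uses a joint Day 29 EOT/ET column and has no row for giving drug at any visit, so it neither orders the dose nor exempts anyone from it.

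2. **Is the missing condition just house style?** No. Section 6.1.8 writes conditions where they are wanted: "Obtain ECG (12-lead) if abnormal findings were observed at Visit 5 (Day 29"), and safety laboratory tests only if needed to follow up adverse events. The gap in 6.1.4 is an omission.

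3. **Do the stop rules close the gap?** In substance, largely. They cover pregnancy and CDAD expressly, and the pregnancy test is listed before the dose in 6.1.4. But none is written as an exception to the ET list, so the two sets of instructions conflict on their face.

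4. **Which visit does 6.1.10 mean?** Its sentence goes on to require all the EOT assessments, and EOT is Visit 5 everywhere else. The number is wrong and the name is right.

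5. **Literal burden at the ET visit:**
   - Dose: 2 × 20 mg = 40 mg, or 4 × 20 mg = 80 mg, by dose group (5.3, Table 1). Placebo subjects would take the same 2 or 4 capsules without active drug.
   - Post-dose draws at 0.5, 1, 1.5, 2, 3, 4, 5 and 8 h: 8 draws.
   - With the carve-out: 0 doses and 0 post-dose draws. The other ET assessments stay.

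**The case against.** The strongest reply is that no competent site would re-dose such a subject. The stop rules are explicit for pregnancy and CDAD. Emergency unblinding means "the subject will be removed from the study", which in plain reading ends dosing. In 7.3, "Temporarily withheld study drug, Permanent discontinuation of study drug" are options for recording an action taken on a vaso-occlusive crisis, and permanent discontinuation already means no more drug. The synopsis, 5.3 and Appendix 2 tie the final dose to Day 29. It can also be said that swallowing capsules is not an assessment. That last argument is weak, because 6.1.4 introduces the whole list, dose included, as assessments to be completed. The rest stands, and it is why the risk is small. It does not remove the conflict in the text.

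A reader might infer four stronger things, which the documents do not support:

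- **That held subjects are routed to the ET list.** Sections 3.1, 4.5 and 6.1.10 speak of discontinuation or withdrawal. A subject on a temporary hold reaches Visit 5 on the ordinary schedule.
- **That the wrong number leaves early leavers with no post-baseline ECG.** Section 6.2.3.5 and Appendix 1 require an ECG at EOT/ET, 4.5 sends discontinued subjects to the ET assessments, and the 6.1.10 sentence itself asks for all EOT assessments.
- **That each ET subject faces 13 PK samples (1 + 8 + 4) and three further visits.** Visits 6 to 8 are fixed to Days 30 to 32. For an ET on Day 12, say, returning on Day 30 is 18 days later, not 24 hours after a dose. The full post-final-dose schedule does not carry over to an early leaver.
- **That the Day 29 steady-state PK is compromised.** Section 8.5.4 uses Days 1 and 29 to 32, so this needs a subject already off drug who attends near Day 29 and is re-dosed. That is too narrow a hypothetical to justify changing 8.5.4, and 8.0 leaves detailed methodology to a separate SAP.

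**Conclusion.** The point holds as a minor internal inconsistency, wrong as written. It is not a design choice: nothing suggests that anyone meant to re-dose subjects taken off drug. The ET list orders a dose and post-dose draws without condition, 4.5 sends every withdrawn or discontinued subject to it, and 6.1.10 misnumbers the visit.

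The size is at most one 40 or 80 mg dose and eight draws per affected subject at that visit. The plan gives no withdrawal rate, so neither the number affected nor any effect on results can be stated. The low risk rests on one assumption: that sites would follow the stop rules over the visit list.

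**What to change.** Make two wording edits.

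- In 6.1.4, mark the final dose, the post-dose PK draws and Visits 6 to 8: *only for subjects still on study drug at Day 29; omit if study drug has been permanently discontinued, is on hold for safety, or the urine pregnancy test at this visit is positive.* The hold clause is there because a held subject attends Visit 5 on schedule and the site needs an answer.
- In 6.1.10, replace *Visit 9 (EOT)* with *Visit 5 (EOT/ET)*.

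Nothing changes for subjects still on drug at Day 29, unless the pregnancy test that day is positive. The cost falls on subjects who are off drug but stay in follow-up: they lose the Day 31 biomarker and safety laboratory set in 6.1.6, along with the vital signs and event checks at Visits 6 to 8. The Day 31 biomarker blood samples are timed 48 hours after a final dose that these subjects would not have taken. The Visit 5 and Day 43 biomarker sets are kept. No new PK sample and no change to 8.5.4 is needed.
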